8 INTERVENTION DISCONTINUATION

This is a one-year pilot study to establish feasibility with low anticipated risk. If there were unanticipated serious adverse events that were possibly or probably related to the study, we would review with the institutional review board and consider discontinuation.

9 STATISTICAL CONSIDERATIONS

9.1 General Design Issues

Aim 1 Demonstrate the feasibility of identifying a diverse cohort of eligible patient/care partner dyads and implementing the PPC program by trained facilitators (e.g. social worker, nurse, nursing assistant). A total of 160 patients or patient-care partner dyads (~50% White, 45% Black, and of those 6% Hispanic/Latino) will be identified as eligible from the geriatrics or primary care practices of three health care systems. Eligible PLWDM and their care partners will be identified through the EHR. Implementation endpoints demonstrating feasibility will include:

1. Identification of care partners for 50% of eligible PLWDM identified in Aim 1,
2. Documentation of PPC discussion in 35% of eligible participants in the EHR, which will be ascertained using review of electronic medical records and an established Natural Language Processing model,
3. Evaluation of implementation endpoints (acceptability, appropriateness, feasibility, fidelity, and potential for future adoption of the intervention) assessed through chart review and semi-structured participant interviews with some patients, patient-care partner dyads, facilitators, and clinicians.

Aim 2 Demonstrate feasibility of pragmatically assessing the following clinical outcomes using the EHR among enrolled patients and patient-care partner dyads measured up to 2 months (60 days) after documented PPC discussion:

1. days at home (primary clinical outcome),
2. total medications, and
3. new referrals to specialist physicians.

We have defined the “days at home” variable to include data two months (60 days) prior (pre-visit days at home) to the PPC visit, as well as two months (60 days) after the visit (post-visit days at home). Days at home are days that are spent at home instead of in a hospital or long-term care facility.

Aim 3 Examine key feasibility measures across racial, ethnic, and socioeconomic subgroups including:

1. quantitative measures of enrollment of eligible dyads, documented PPC discussions, and clinical outcomes measures, and
2. Qualitative measures ascertained from chart review and participant interviews, including acceptability and appropriateness.
3. Deploy established algorithms for detecting social factors that may influence patient care priorities, such as housing instability, financial insecurity, or transportation concerns. These algorithms have been previously created and

validated across the care spectrum and will be deployed at the primary site in current form on the established natural language processing platform at Regenstrief Institute. All available clinical notes for the recruited cohort will be annotated by the software as either positive or negative for the social factors. This can then be incorporated into analyses.

Given the smaller recruitment size for the secondary site, keywords from the algorithms will be shared with the study team for manual chart extraction. This process will also be utilized as controls for the programmatic implementation at the primary site.

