We will use findings from Aim 3 to examine key feasibility measures across racial, ethnic, and socioeconomic subgroups to determine further adjustments that may be needed to tailor the intervention to a diverse population. We recognize that a “one size fits all” approach is inappropriate for many historically and structurally marginalized groups and that adjustments may need to be made to the flexibility of the overall intervention protocol. This may include identification of additional implementation or clinical endpoints for examination. Progression criteria for this aim is that we are able to determine the key feasibility measures for a minimum of the +/- 10% proportion of racial, ethnic, and socioeconomic subgroups that mirrors the populations seen in each health system. We will also conduct between-group comparisons on our measure of PPC documentation between Black v. White and those with financial insecurity vs. none (small sample sizes will preclude analysis of Hispanic patients and those with housing instability). If there are significant differences, we will make further adjustments prior to embarking upon a Stage IV ePCT of this intervention.

Table 1. Implementation outcomes and data sources		
	Implementation outcomes	Source of data
Feasibility	Identification of sample Enrollment goals Feasibility of outcome ascertainment	Administrative data Qualitative interviews with clinicians, patients, and care partners NLP

Adoption	Utilization /intent to use	EHR Qualitative interviews with clinicians
Acceptability / appropriateness	Satisfaction with the intervention (content, delivery, credibility) Perceived usefulness and practicality	Qualitative interviews with clinicians, patients, and care partners
Fidelity	Adherence to implementation protocol Quality of implementation	Training records – completion /results- competency Checklist of adherence to protocol -EHR Qualitative interviews- barriers /facilitators to refine implementation strategy

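### The financial-insecurity flag has no note cut-off before PPC contact, so a PPC note can help form the groups in which PPC documentation is compared

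*Protocol*

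**What the plan says.** Protocol 9.1, Aim 3 item 3, plans algorithms for "detecting social factors that may influence patient care priorities, such as housing instability, financial insecurity, or transportation concerns". They "will be deployed at the primary site in current form on the established natural language processing platform". The source text is described as follows: "All available clinical notes for the recruited cohort will be annotated by the software as either positive or negative for the social factors". The next sentence is permissive: "This can then be incorporated into analyses". At the secondary site, "keywords from the algorithms will be shared with the study team for manual chart extraction". Neither route has a note window.

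Protocol 9.4.2 plans comparisons of PPC documentation "between Black v. White and those with financial insecurity vs. none", with this consequence: "If there are significant differences, we will make further adjustments prior to embarking upon a Stage IV ePCT of this intervention".

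Four other places bear on timing:

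- The Précis (intervention step 6) and 5.2 (step 5) say that data other than outcomes come from the two years before the clinic visit, and outcomes from the two months after it.
- The Précis and 5.1 allow the facilitator conversation (Step 1) either one to two weeks before the visit or alongside it.
- Section 5.4 reads PPC documentation from clinical text, including the words after the PPC dot phrase.
- Section 6.2.2 treats packet mailing as enrolment and assesses documentation about 60 days after the visit.

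The SAP compares ethnicity, race, sex and age between patients with and without a documented conversation. It does not name or define financial insecurity.

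**The concern.** A subgroup variable should be fixed before the outcome can influence it. Here the outcome is whether a PPC conversation was charted, and the grouping variable is read from the chart. The protocol chose these social factors because they may bear on care priorities, which is what a PPC conversation is about. A patient with a charted conversation therefore has at least one extra note in which money worries could be recorded. If such notes count, some documented patients move into the flagged group because they were documented.

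The error runs in one direction whenever documented patients gain more new flags than undocumented ones: documentation looks higher among the financially insecure. For an equity question this is the harmful direction. A true deficit can shrink, vanish or reverse, and 9.4.2 would then give no signal to adapt the intervention. The Précis and 2.2 make evidence that socioeconomic groups are equally engaged a condition for moving to the full trial.

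**Working it through.** **1. Which notes can count under each reading of the text**

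| Reading | PPC notes that can set the flag |
|---|---|
| 9.1 taken literally | Step 1 and Step 2 notes, and any later note |
| Two-year pre-visit window (Précis, 5.2) governs | Step 1 notes written one to two weeks before the visit |
| Cut-off the day before packet mailing (not in the plan) | None |

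Neither reading that the documents allow removes every PPC note.

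**2. The plan's own figure**

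The plan gives no figure for this comparison. Its sample size of 160 (9.2) is for a one-sample test of 40% against 50% at 80% power. Taking one-sided 5% (not stated), an exact binomial rule at n = 160 with success at 75 or more has error 0.046 and power 0.808, so 160 reproduces. It was not chosen for the subgroup comparison and serves below only as an input.

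**3. Model**

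- n = 160 (9.2); p = 0.35 documented (the 9.4.2 target), equal in both groups, so there is no true difference.
- b = share flagged from earlier notes: assumed 0.20, range 0.15 to 0.30.
- a = chance that a documented, previously unflagged patient gains a flag: assumed 0.05 to 0.15.
- u = the same chance for an undocumented patient: first 0, then above 0.
- Two-sided Fisher test. The SAP gives the sidedness and names this test for its categorical variables; the 5% level is assumed.

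Let d = b + (1−b)a and e = b + (1−b)u. Then

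- documented among flagged = pd / [pd + (1−p)e]
- documented among unflagged = p(1−d) / [p(1−d) + (1−p)(1−e)]

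Worked case, b = 0.20, a = 0.10, u = 0: d = 0.28 and e = 0.20. Flagged: 0.098 / (0.098 + 0.130) = 43.0%. Unflagged: 0.252 / (0.252 + 0.520) = 32.6%. False gap: 10.3 points before rounding.

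**4. Results with no true difference (b = 0.20)**

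| a | u | Flagged | Unflagged | False gap (points) | Fisher rejects |
|---|---|---|---|---|---|
| 0 | 0 | 35.0% | 35.0% | 0 | about 4% |
| 5% | 0 | 39.3% | 33.8% | 5.4 | about 7% |
| 10% | 0 | 43.0% | 32.6% | 10.3 | about 18% |
| 15% | 0 | 46.3% | 31.4% | 14.9 | about 35% |
| 10% | 5% | 38.6% | 33.8% | 4.8 | about 7% |
| 15% | 10% | 38.1% | 33.7% | 4.4 | about 8% |

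Rejection rates come from 20,000 simulated trials per row. With u = 0, b from 0.15 to 0.30 and a from 5% to 15%, the false gap runs from 3.7 points (b = 0.30, a = 5%) to 18.5 points (b = 0.15, a = 15%).

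**5. Masking a true deficit**

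Assume true documentation of 20% in the 20% who are financially insecure and 38.75% in the rest (overall 0.2 × 20% + 0.8 × 38.75% = 35%), with u = 0.

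| a | Flagged | Unflagged | Apparent gap (points) | Chance of a significant deficit |
|---|---|---|---|---|
| 0 | 20.0% | 38.75% | −18.75 | about 48% |
| 5% | 25.8% | 37.5% | −11.8 | about 21% |
| 10% | 30.7% | 36.3% | −5.5 | about 7% |
| 15% | 35.1% | 35.0% | +0.1 | about 2% |

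**The case against.** Five points can be made for the plan.

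- **Notes, not patients.** Section 9.1 annotates notes and gives no rule for turning them into a patient-level group. Annotating everything is compatible with later using only early notes. This stands: the plan leaves the rule open and does not state a circular one.
- **No explicit link.** No section says that the annotations form the financial-insecurity groups in 9.4.2. This also stands. However, it is the only source of such a variable that the documents describe, and 9.4.2 mentions financial insecurity alongside housing instability, two of the factors in 9.1.
- **The pre-visit window.** A subgroup variable is not outcome data, so the two-year window may govern. It would then remove visit-day and later notes, which is a real limit. Step 1 notes from one to two weeks earlier would remain. If half of those conversations took place before the visit (an assumption), the 10% case would fall to 5% and the false gap from about 10 points to about 5.
- **Undocumented patients also have notes.** Under the literal wording they can gain flags too, and the last two rows of the first results table show how far this shrinks the gap.
- **Limited stakes.** This is a secondary comparison in a pilot, and a significant result leads to adjustments, not to stopping. That bears on priority; it does not remove the bias.

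A reader might infer that the flag is in fact set by PPC notes and that the comparison is already caused by its own outcome. The documents do not say so. They permit it.

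**Conclusion.** The concern holds as a conditional one. The plan does not confine the financial-insecurity flag to notes that predate PPC contact. If that flag forms the groups in 9.4.2, the comparison can be contaminated by its outcome, towards higher documentation among flagged patients. The pre-visit window narrows the problem if it applies, but does not close it.

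The size cannot be derived from the documents. The gaps of about 5 to 15 points and rejection rates of about 7% to 35% rest on an assumed 20% baseline flag rate, new flags only among documented patients, and the no-cut-off rule acting across all 160 patients. They illustrate the less favourable side. What counts is the excess of new flags in documented over undocumented patients, and a 5-point excess gives about 4 to 5 points. With no new flags after the cut-off, this bias is absent. The change is worth making because a decision depends on the comparison and the remedy is cheap.

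**What to change.** In Protocol 9.1 and the SAP:

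1. Define a patient-level financial-insecurity flag from notes dated in the two years up to the day before the PPC packet was mailed, including how note-level annotations combine into one value per patient.
2. Apply the same window at all sites, to both the software annotation and the manual keyword extraction.
3. State that this flag forms the groups in 9.4.2, and add that comparison to the SAP.
4. Reconcile the all-notes wording in 9.1 with the two-year window in the Précis and 5.2.
5. Report factors first recorded from mailing onwards descriptively only, and do not use them to form groups.

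Mailing is a natural cut-off because 6.2.2 already treats it as enrolment, and a two-year look-back is already planned. Excluding PPC notes by type could also work, but it depends on recognising every such note. The cost is a date filter on the software output, a date check during manual extraction, a few sentences of text, and slightly fewer flagged patients.

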9.2 Sample Size and Randomization

While pilot studies typically do not warrant power calculations, a target sample size can be estimated to ensure the results support progression to a full trial. Based on Lewis et al.'s red zone/green zone criteria, with an anticipated proportion for the upper red zone cut-off of 40% and the lower green zone cut-off of 50% for a one-sample test and 80% power (Aim 1), 160 dyads is suggested as a sample size for the proposed study. To meet criteria for progression to a full ePCT, we will aim to meet the recruitment goals described below for each implementation outcome. In alignment with discussions with the IMPACT Collaboratory Consultation Team, we will not be randomizing for this study. We will plan in the subsequent Stage IV trial of this intervention to employ a randomized stepped wedge approach.

9.2.1 Treatment Assignment Procedures

Not applicable.

9.3 Interim analyses and Stopping Rules

Not applicable (no interim analysis for this one-year study)

9.4 Outcomes

9.4.1 Primary (clinical) outcome

1. Days at home is the primary clinical outcome we are measuring. We will survey for 2 months (60 days) before the PPC visit (pre-visit days at home), as well as for 2 months (60 days) after the PPC visit (post-visit days at home), utilizing data that is collected from the patient's electronic medical record.

9.4.2 Secondary (implementation) outcomes

1. Identification of care partners for 50% of eligible PLWDM,
 - To meet green zone criteria, we must identify care partners for 50% of eligible PLWDM.
 - The red zone threshold is 40%.
 - Should the sample fall in the amber zone between 40-50%, then we will determine whether acceptable amendments can be made to the protocol to warrant progression to a full ePCT.

2. Documentation of PPC discussion in 35% of eligible participants in the EHR, which will be ascertained using an established Natural Language Processing model,
 - To meet green zone criteria, we must identify PPC discussion in 35% of eligible participants. In the original study of PPC, 66.3% of visit notes indicated a PPC discussion. Because that was performed at a single institution under ideal conditions, we expect that our pragmatic pilot will have a lower recruitment rate for this aim than the original study. That said, the 65% green zone is associated with a sample size of 159 individuals, which would include our overall recruitment goal.
 - Should the sample fall in the amber zone between 25-35%, then we will determine whether there are amendments that can be made to the protocol to warrant progression.
3. Evaluation of implementation endpoints (acceptability, appropriateness, feasibility, fidelity, and potential for future adoption of the intervention) assessed through chart review and semi-structured participant interviews with some patients, patient-care partner dyads, facilitators, and clinicians (Table 1).

If themes emerge that indicate potential future successful full ePCT, then this will meet progression criteria.

We will use findings from Aim 3 to examine key feasibility measures across racial, ethnic, and socioeconomic subgroups to determine further adjustments that may be needed to tailor the intervention to a diverse population. We recognize that a “one size fits all” approach is inappropriate for many historically and structurally marginalized groups and that adjustments may need to be made to the flexibility of the overall intervention protocol. This may include identification of additional implementation or clinical endpoints for examination. Progression criteria for this aim is that we are able to determine the key feasibility measures for a minimum of the +/- 10% proportion of racial, ethnic, and socioeconomic subgroups that mirrors the populations seen in each health system. We will also conduct between-group comparisons on our measure of PPC documentation between Black v. White and those with financial insecurity vs. none (small sample sizes will preclude analysis of Hispanic patients and those with housing instability). If there are significant differences, we will make further adjustments prior to embarking upon a Stage IV ePCT of this intervention.

Table 1. Implementation outcomes and data sources		
	Implementation outcomes	Source of data
Feasibility	Identification of sample Enrollment goals Feasibility of outcome ascertainment	Administrative data Qualitative interviews with clinicians, patients, and care partners NLP

Adoption	Utilization /intent to use	EHR Qualitative interviews with clinicians
Acceptability / appropriateness	Satisfaction with the intervention (content, delivery, credibility) Perceived usefulness and practicality	Qualitative interviews with clinicians, patients, and care partners
Fidelity	Adherence to implementation protocol Quality of implementation	Training records – completion /results- competency Checklist of adherence to protocol -EHR Qualitative interviews- barriers /facilitators to refine implementation strategy

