4.1 Inclusion Criteria

Patient Inclusion Criteria

Patients must meet all of the following criteria to participate in this study:

- 40 years or older
- English-speaking
- Receiving care with a participating physician
- Has a scheduled outpatient care visit within 1-2 months (60 days)
- Individual has a diagnosis of MCI or dementia

Definition: To identify individuals with dementia and MCI, we will use two or more instances of use of an ICD-10 code for either diagnosis in the EHR within 24 months. Typically, we would include instances of these billing codes within a year of each other but, due to the COVID-19 pandemic, recognize that there may be less frequent clinical visits and less robust billing. Diagnostic codes include:

- F01.50, F01.51, F02.80, F02.81, F03.90, G30.0, G30.1, G30.8, G30.9, G31.01, G31.09, G31.1, G31.2, F41.81, G31.84 and F03.91.

Care Partner Inclusion Criteria

Care partners must meet all of the following criteria to participate in the study:

- 18 years or older
- English-speaking

A note about inclusion of care partners: Clinician determination of a patient's capacity to participate in a visit independently is part of a pragmatic approach. This means that clinic staff will determine when a care partner is needed. Generally, we act under the assumption that patients who require a care partner will have already included them in previous visits and/or provider communications (and we anticipate that this will be documented in the EHR), whereas patients who attend clinic visits independently and have no documentation indicating the involvement of a care partner in their medical

decisions, or a need for one, will be determined to have the capacity to also participate in a PPC visit.

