6.2.2 Enrollment, Baseline, and/or Randomization

Enrollment

Due to the nature of the PPC model, there is no formal enrollment procedure or baseline research interview. Rather, patients will be considered enrolled if they meet inclusion criteria and a PPC packet is mailed to them.

- Note: a patient may decline to participate in the PPC intervention at any time. Declining to receive the PPC intervention will in no way impact their clinical care that patients receive now or in the future.
 - Individuals who inform their provider or other clinical staff that they wish to decline to receive the PPC intervention will be excluded from the enrolled patient list and will not be included in outcomes assessments for the study.

Baseline Assessments

The clinic visit is the reference point by which we will assess patient outcomes.

The PPC conversation will include two steps:

1. Priorities identification with a facilitator
2. Alignment of patient priorities with their medical care plan in collaboration with their physician or advanced practice provider(s).

Consistent with local clinical practices, the facilitator and clinician will be identified by clinic leadership for each eligible participant. A facilitator for the

first step of the intervention may be any member of the clinical team. The clinician in the second step must be the patient's physician or advanced practice provider.

Because the primary outcome is documentation in the EHR, the assessment for documentation will occur approximately two months (60 days) after the patient's clinic visit.

Randomization

Not applicable

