We will approach providers who have participated in PPC implementation by phone, email, or in person during clinic to invite them to complete a semi-structured interview with research staff. There will be no penalties for declining to participate in the interview. For those who are interested, we will conduct informed consent as outlined above.

Documentation of Consent

All research activities including documentation of consent procedures will be recorded in the source document (including the date), by research staff at each clinic before the participant undergoes any study-specific procedures.

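### Adoption has no clinician denominator, and interview evidence on intent to use comes only from clinicians who used or helped implement PPC

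*Protocol*

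**What the plan says.** Protocol section 9.4.2, item 3, sets out the endpoint: "potential for future adoption of the intervention) assessed through chart review and semi-structured participant interviews". Table 1 describes adoption as "Utilization /intent to use" and names two sources, the EHR and clinician interviews. It gives no number of clinicians to divide by and no threshold. Item 3 counts as met for progression if the themes that emerge point to a successful full trial.

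Two sentences in section 11.2 decide who is interviewed. The general paragraph on the PEP Talks makes eligible those who took part in a PPC visit that was documented. The paragraph on facilitators and clinicians says "We will approach providers who have participated in PPC implementation". Section 5.2 expects up to about 30 interviews in all.

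On the patient side, section 4.1 requires "Receiving care with a participating physician". For documentation, section 9.4.2 says "we must identify PPC discussion in 35% of eligible participants", and the next band is introduced with "Should the sample fall in the amber zone between 25-35" per cent. Under section 6.2.2, "patients will be considered enrolled if they meet inclusion criteria and a PPC packet is mailed to them"; patients who decline PPC are "excluded from the enrolled patient list and will not be included in outcomes assessments for the study".

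Training is put to clinical staff as a request (sections 3 and 10.3.1). Training completion is listed in Table 1 under fidelity, not adoption. The SAP compares patient demographics by documentation status and contains no clinician variable.

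**The concern.** Adoption is a property of clinicians: of those who could use PPC, how many do, and how many intend to? Answering that needs a defined set of clinicians and some information from those who did not take it up. The plan provides neither. EHR utilization can show that PPC notes exist, but not what fraction of clinicians wrote them. The interviews, which carry the evidence on intent to use, are directed to people already involved. Reasons for declining, or for completing training and then not using PPC, are the evidence most likely to count against adoption, and they fall largely outside the sample.

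This matters because the interview themes can meet a progression criterion, and the next step is a full embedded trial, planned in section 9.2 as a stepped wedge, in which delivery across clinicians is the practical question.

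A second, conditional issue concerns the 35% target. If participating means that a physician individually agreed, patients of those who did not agree never enter the denominator, and nothing in the plan records how many such patients there are.

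**Working it through.** **Step 1. Which clinicians each data source can see.** I read the eligible participants of section 9.4.2 as the enrolled list of section 6.2.2.

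| Clinician | Patients in the 35% denominator? | Eligible for interview (11.2)? | Counted as a clinician in adoption? |
|---|---|---|---|
| Declines, if participating means opt-in | No (4.1) | No | No |
| Participates, never documents PPC | Yes, as undocumented (6.2.2) | No under the documented-visit sentence; unclear under the implementation sentence | No |
| Participates, documents PPC | Yes | Yes | Notes visible in the EHR, but no denominator |

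The interview gap covers the first row and, at least on the documented-visit sentence, the second. The denominator gap covers only the first row, and only on the opt-in reading.

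**Step 2. The plan's own sample size.** Section 9.2 gives 160 from a one-sample test of 40% against 50% with 80% power. Alpha is not stated; I assume one-sided 0.05.

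- n = [1.645 × √(0.40 × 0.60) + 0.842 × √(0.50 × 0.50)]² / 0.10² = 150.5.
- With continuity correction: (150.5/4) × [1 + √(1 + 2/(150.5 × 0.10))]² = 160.3, which matches 160 after rounding.

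This calculation concerns patients and the 40%/50% cut-offs. It does not bear on clinician uptake. It is used below only as the enrolled count.

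**Step 3. Participating clinicians who never use PPC.** Their patients stay in the denominator once a packet is mailed. If 80% of enrolled patients were under clinicians who use PPC, those clinicians would need a rate of 35/0.80 = 43.75% for the whole sample to reach 35%. Non-use by participants therefore makes the target harder to reach.

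**Step 4. Illustration for physicians who decline.** Let s be the share of otherwise eligible patients under participating physicians (not given in the documents), r the observed rate and q the rate among the other patients. The rate over all otherwise eligible patients is s × r + (1 − s) × q. With r = 35% and q = 0:

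| s | Rate over all otherwise eligible patients |
|---|---|
| 100% | 35.0% |
| 90% | 31.5% |
| 80% | 28.0% |
| 70% | 24.5% |
| 60% | 21.0% |

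The rate equals 25% at s = 25/35 = 71.4%. In counts, 35% of 160 is 56 patients. With 64 further eligible patients under non-participating physicians, 56/224 = 25.0%; with 65, 56/225 = 24.9%. If q = 10%, the rate equals 25% at s = (25 − 10)/(35 − 10) = 60%.

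**The case against.** The strongest reply has four parts.

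First, adoption does not rest on interviews alone. Table 1 names the EHR as a source, and EHR utilization does not depend on who is interviewed; training completion is recorded as well. This stands, so a reader who infers that all the adoption evidence comes from adopters goes too far. But neither source is expressed over a defined set of clinicians.

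Second, a reader might infer that clinicians who take part but never use PPC are hidden behind a 35% result. The documents do not support that: enrollment follows from mailing, and section 4.3 says providers do not pre-screen for the mailing. Step 3 shows that such clinicians lower the rate.

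Third, participation is often described at site level. Clinicians at the three participating sites receive training (section 3), and clinic leadership names the facilitator and clinician for each patient (section 5.1). If everyone at the clinic counts as participating, no patients are lost from the denominator by this route. These passages make a large block of opted-out physicians speculative, but they do not define the term in section 4.1.

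Fourth, the 35% and the 25–35% band are set for eligible participants. The protocol never presents 35% as a clinic-wide rate, and for documentation it writes no red limit; below 25% is only implied by the amber band. This also stands, so the cut-offs should not be applied to a clinic-wide figure.

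None of these replies supplies a clinician count or brings decliners into the interviews.

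**Conclusion.** The point holds for the adoption measure. EHR utilization lacks a clinician denominator, and the interview evidence on intent to use is selected on use or involvement while being able to meet a progression criterion. This follows from sections 9.4.2 and 11.2 without any numerical assumption.

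The effect on the documentation rate is conditional and its size is unknown. It arises only if participating means individual opt-in. The 71.4% figure further assumes an observed rate of exactly 35% and no PPC documentation among other patients.

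A reader might go on to infer that a green result conceals a red-zone clinic. The documents do not support that conclusion: they give no participation share, they do not say that physicians opt in one by one, and they set no cut-off for a clinic-wide rate. What they do leave open is the meaning of the term and the number of patients it removes.

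The change needed is to reporting and interview sampling; the sample size and progression thresholds can stay as they are.

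**What to change.** - Before the first mailing, fix a list for each clinic of all physicians and advanced practice providers who see patients meeting the other criteria in section 4.1.
- In section 9.4.2 and Table 1, report adoption per site as the number and proportion of that list who agreed, who completed training, and who had at least one documented PPC discussion. Training records and EHR data are already planned.
- Amend both interview sentences in section 11.2 so that some clinician interviews, within the total of about 30, go to clinicians who declined or never documented PPC.
- State in section 4.1 whether participating means individual opt-in. If it does, give beside the 35% result the number of otherwise eligible scheduled patients under non-participating clinicians. Keep this descriptive: do not apply the 35%/25% cut-offs to a clinic-wide rate, and do not multiply the observed rate by a participation share, since that builds in the assumption of no PPC elsewhere.

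The cost is one clinician list per clinic, an extra count from the schedule review if opt-in applies, and a few of the planned interviews redirected. The adoption figure may look less favourable than it otherwise would.
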